8.4.1 Vital Signs

Vital signs will be summarized descriptively for each treatment group at each visit. The within group CFBs will be summarized and will be compared with a paired t-test by visit; the between-group difference for each visit will be compared with an ANOVA, and two-sided 95% CI for the differences between each of the treatment groups and the placebo group will be presented.

A by-subject listing of vital signs will be provided.

8.4.2 Physical Examination

Physical examination abnormal findings will be summarized by treatment group and body system.

A by-subject listing of abnormal physical examination findings will be provided.

8.4.3 12-Lead ECG

ECG parameters, i.e., HR, PR, QT, QRS, QTcF, and QTcB will be summarized descriptively for each treatment group at each visit. The within-group CFBs will be summarized and will be compared with a paired t-test by visit; the between-group difference for each visit will be compared with an ANOVA, and two-sided 95% CI for the differences between each of the treatment groups and the placebo group will be presented.

The number and percentage of subjects with abnormal, clinically significant (CS) finding will also be summarized by treatment group at each visit.

ECG data will be listed by subject and visit including changes from baseline.

A summary of the number and percentage of subjects with QTcF intervals exceeding some predefined upper limits (e.g., >450ms, >480ms, >500ms for measured values as well as. >30ms, >60ms for CFBs) will be displayed in a frequency table.

8.4.4 TVU Assessments

TVU data will be summarized descriptively for each treatment group at each visit. CFBs in the number and/or size of ovarian cysts, changes in endometrial thickness will be summarized.

A by-subject listing of TVU findings will be provided.

8.4.5 DXA Scan

Bone mineral density data from DXA scan will be summarized descriptively for each treatment group at each visit. The within-group %CFB will be summarized and will be compared with a paired t-test by visit; the between-group difference for each visit will be compared with an ANOVA, and two-sided 95% CI for the differences between each of the treatment groups and the placebo group will be presented. Data from post treatment Month 6/Month 12 (before Protocol version 5.0) will not be analyzed for clinical study report (CSR).

In addition, DXA scan will be summarized for each treatment group by category the %CFB as $\geq -3\%$, $-3\% \text{ to } -5\%$, $-5\% \text{ to } -8\%$ and $<-8\%$.

A by-subject listing of DXA scan data will be provided.

8.4.6 Mammogram

Mammogram is required for females aged ≥ 40 only in the US and Poland sites. A by-subject listing of mammogram results will be provided.

8.4.7 Cervical Cytology Test

Cervical cytology will be assessed at any time during the Screening period. Collected data will be listed.

8.4.8 Sellar MRI with Contrast

Sellar MRI will be assessed at any time during the Screening period. Collected data will be listed.

8.5 Safety Monitoring (Independent Data Monitoring Committee [IDMC])

In order to monitor and protect the safety of study subjects, an IDMC will be established to review all study data pertaining to subjects' safety on regular basis to adjudicate the overall safety of the subjects in this study. The IDMC will convene to provide recommendations on study design and IMP based on review of unblinded safety data. The IDMC will consist of unblinded experts in the fields of gynecology and one independent unblind biostatistician.

In addition, the IDMC will be notified, and a meeting may be called for each case of IMP discontinuation due to an IMP related safety reason.

Study will be paused pending prompt review by IDMC if 2 or more subjects experience similar SAE or severe AE assessed as related to IMP or discontinue IMP for safety reasons assessed as related to IMP.

Study will be paused if any of the following assessed as related to IMP occurs, pending prompt review of the case(s) by the IDMC: death, suicide attempt, serious changes in behavior (such as psychosis or the development of impulse control disorders or addictive behavior), cardiac arrhythmia or AEs pertaining to the pituitary gland.

Refer to the DMC Charter for further details.

9. OTHER ANALYSES

9.1 Pharmacokinetics

9.1.1 Pharmacokinetic Concentrations

PK concentration data for HMI-115 will be listed by treatment and subject. Listings will include nominal PK sampling time, actual sampling times relative to dose administration, deviation from nominal time, and concentration. Concentrations below the lower limit of quantification (LLOQ) will be presented as below the limit of quantification (BLQ) in the listings. Any PK data excluded from PK analysis set will be identified.

Separate concentration for HMI-115 summary tables will be included for intensive and sparse PKS. Concentrations will be summarized by treatment group and nominal timepoint. The following descriptive statistics will be presented for concentrations obtained at each nominal time point: N (number of subjects who received treatment), n (number of subjects with non-missing values), and n (BLQ) (the number of subjects with BLQ samples), arithmetic mean, SD, coefficient of variation (CV%), geometric mean (Geomean), geometric CV% (calculated as: $gCV\% = \text{SQRT}(es^2 - 1) * 100$; where s is the standard deviation of the log-transformed values), median, minimum and maximum values.

For summary tables, all BLQs will be considered zero. Summary Statistics will not be calculated if non-BLQ concentrations at a scheduled time point is < 3 and will be reported as "not calculable (i.e., NC)".

The following rules will be followed with regards to the number of decimal places and presentation of data in the tables and listings of concentration data:

Concentration Listings and Tables	Rounding
Individual concentrations	n s.f. as supplied by bioanalytical laboratory No rounding
Minimum and Maximum	n s.f. capped at 4
Mean/SD/Median/Geomean	$n+1$ s.f. capped at 4
CV%/gCV%	1 d.p.
N/n	Whole number

s.f. = significant figures, d.p. = decimal place

For arithmetic mean graphs, separate figures will be created for extensive and sparse PKS. For linear/linear graphs all BLQ values will be substituted with zero for calculation of arithmetic mean and for log/linear graphs the log transformed arithmetic mean will be displayed (this should not include zero).

For individual linear/linear and log/linear graphs all BLQ values will be substituted as follows:

- BLQs at the beginning of a participant profile (i.e., before the first incidence of a measurable concentration) will be assigned to zero. When using log/linear scale, these timepoints will be considered missing.
- BLQs at the end of a participant profile (i.e., after the last incidence of a measurable concentration) will be set to missing.
- Single BLQs which fall between two measurable concentrations will be set to missing.
- Consecutive BLQs which fall between measurable concentrations will be set to missing. Measurable concentrations after consecutive BLQs will be set to missing.

To visualize the comparison between each treatment, the following descriptive PK graphs will be generated for intensive and sparse PKS.

- Figure 1: Individual Profile for HMI-115 Plasma Concentration Time Data – Linear Scale

- Figure 2: Individual Profiles for HMI-115 Plasma Concentration Time Data – Semi Logarithmic Scale
- Figure 3: Overlaid Individual Profiles for HMI-115 Plasma Concentration Time Data by Treatment – Linear Scale (Spaghetti Plots, only intensive PKS)
- Figure 4: Overlaid Individual Profiles for HMI-115 Plasma Concentration Time Data by Treatment – Semi-Logarithmic Scale (Spaghetti Plots, only intensive PKS)
- Figure 5: Mean (\pm SD) HMI-115 Plasma Concentration Time Data by Treatment and by PKS Subset (intensive and sparse) – Linear scale (including a separate plot for subgroup – Asian vs. Others)
- Figure 6: Mean HMI-115 Plasma Concentration Time Data by Treatment and by PKS Subset (intensive and sparse) – Semi-Logarithmic Scale (including a separate plot for subgroup – Asian vs. Others)
- Figure 7: Boxplot of C_{trough} Time data by Treatment and by PKS Subset (intensive and sparse) – Linear Scale (including a separate plot for subgroup – Asian vs. Others)

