9.1.2 Pharmacokinetic Parameters

PK parameters will be calculated for the intensive PKS by non-compartmental analysis methods from the concentration-time data following these guidelines:

- Actual sampling times relative to dosing rather than nominal times will be used in the calculation of all derived PK parameters.
- There will be no imputation of missing data.
- Handling of BLQ samples for derivation of PK parameters
 - Day 1, all BLQ values pre-dose and in the absorption phase prior to the first quantifiable concentration will be substituted by zeros.
 - For subsequent dosing days, BLQ values pre-dose, in the absorption phase, and between evaluable concentrations will be substituted by missing values before the calculation of the PK variables.
 - BLQs at the end of a participant profile (i.e., after the last incidence of a measurable concentration) will be set to missing.

Pharmacokinetic parameters will be estimated according to the following guidelines:

Parameter	Guideline for Derivation
C_{max} , t_{max} , C_{trough} ,	Obtained directly from the observed concentration-time data
AUC_{0-10d} , AUC_{0-inf} , $AUC_{(0-tau)}$	The AUC_{0-10d} , AUC_{0-inf} , AUC over the dosing interval after the last administered dose will be calculated by a combination of linear and logarithmic trapezoidal methods. Unless specifically requested and justified, the linear up/log down trapezoidal method will be employed.
%AUCextrap	Percentage of AUC_{inf} (obs, pred) due to extrapolation from t_{last} to infinity: $\%AUCextrap = \frac{AUC_{inf} - AUC_{last}}{AUC_{inf}} * 100$

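### The BLQ rules leave the geometric statistics in the concentration tables undefined and remove BLQ troughs from the intensive-subset Ctrough summary, which biases that summary upward

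*SAP*

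**What the plan says.** **Concentration tables (SAP 9.1.1, intensive and sparse sets).** The rule is "For summary tables, all BLQs will be considered zero". The statistics required at each nominal time include "n (BLQ) (the number of subjects with BLQ samples), arithmetic mean, SD, coefficient of variation (CV%), geometric mean (Geomean") and a geometric CV, "where s is the standard deviation of the log-transformed values". One suppression rule applies: "Summary Statistics will not be calculated if non-BLQ concentrations at a scheduled time point is < 3". No sentence says how zeros enter the two geometric statistics. For mean graphs on a log scale, the same section does say that zeros are to be left out.

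**NCA parameters (SAP 9.1.2, intensive set only).** BLQs before the first quantifiable value on Day 1 become zero. After that, "For subsequent dosing days, BLQ values pre-dose, in the absorption phase, and between evaluable concentrations will be substituted by missing values" before the PK variables are calculated, and "BLQs at the end of a participant profile (i.e., after the last incidence of a measurable concentration) will be set to missing". Missing data are not imputed. Ctrough is "Obtained directly from the observed concentration-time data". The parameter summary shows N and n but no BLQ count.

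**Plots.** SAP 9.1.1 Figure 7 (Ctrough boxplot, both PK subsets) and SAP 9.1.3 (Ctrough against pain scores and prolactin) have no BLQ rule of their own. For individual concentration graphs, SAP 9.1.1 adds: "Measurable concentrations after consecutive BLQs will be set to missing".

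**The concern.** There are two separate faults.

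1. The concentration table asks for log-scale statistics on data that may contain zeros. The programmer has to improvise, and different choices give very different printed values.
2. The same BLQ trough counts as zero in the concentration table and as absent in the Ctrough parameter summary. The second treatment removes the lowest values from a summary meant to describe trough exposure.

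The second fault bears on the dose rationale. Protocol 4.3.2 argues from the lower tail: a trough above 10 mg/L is thought necessary for maximum effect, and 240 mg Q2W is put forward so that every subject reaches 12 mg/L. A summary without the lowest troughs cannot test a statement about every subject. It would also hide a subject who lost exposure through anti-drug antibodies, although Protocol 8.10 pairs ADA samples with PK samples.

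**Working it through.** The plan states no figure to reproduce: it gives no LLOQ and no expected BLQ rate. The sizes below are illustrations.

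**Inputs**
- Intensive subset: n = 10 per arm (Protocol 4.1).
- Predicted steady-state Ctrough at 240 mg Q2W: geometric mean (GM) 27.3 mg/L, 90% interval 12.0 to 61.4 (Protocol Table 4-2).
- Assumed LLOQ: 0.05 to 1.0 mg/L.
- k = number of BLQ values among n.

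**Step 1: spread.** Log-SD = ln(61.4/12.0)/(2 × 1.645) = 0.496. Check on log-normality: √(12.0 × 61.4) = 27.1, against the stated 27.3. Arithmetic mean (AM) of measurable values = 27.3 × exp(0.496²/2) = 30.9 mg/L.

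**Step 2: when the table rule fails.** NC applies only below three measurable values. With n = 10, the geometric statistics therefore have no valid definition for k = 1 to 7.

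**Step 3: possible readings of the concentration table, k = 2**

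| Treatment of zeros in the geometric statistics | GM (mg/L) | AM beside it, BLQ = 0 (mg/L) |
|---|---|---|
| Product form, zeros kept | 0 | 0.8 × 30.9 = 24.7 |
| Log form, zeros kept | undefined | 24.7 |
| Zeros discarded by software | 27.3 (8 subjects) | 24.7 (10 subjects) |

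The last row prints a geometric mean above the arithmetic mean, which cannot happen within one set of values.

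**Step 4: Ctrough parameter summary.** Let S be the sum of the measurable troughs. With BLQ missing the mean is S/(n−k); with BLQ as zero it is S/n. The ratio is n/(n−k), whatever the distribution:
- k = 1: 10/9 = 1.11
- k = 2: 10/8 = 1.25
- k = 3: 10/7 = 1.43

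Zero is itself a convention, but this matters little. For k = 2 and true values as high as an LLOQ of 1.0, the mean is (8 × 30.88 + 2 × 1.0)/10 = 24.9, and 30.88/24.9 = 1.24.

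**Step 5: the geometric mean of Ctrough.** With BLQs missing it stays at 27.3 for any k. With LLOQ/2, GM = exp{[(n−k) ln 27.3 + k ln(LLOQ/2)]/n}:
- k = 1: 13.6 (LLOQ 0.05) to 18.3 (LLOQ 1.0), so the missing rule gives a value 2.0 to 1.5 times as high.
- k = 2: 6.7 to 12.3, so 4.1 to 2.2 times as high.

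**Step 6: can BLQs occur?** Under the predicted 240 mg steady-state distribution, the probability of a trough below even 1.0 mg/L is about 1.3 × 10⁻¹¹, so chance alone will not produce one. Washout samples differ. Protocol 4.4 says Week 25 covers five half-lives, and Table 1-2 places it 98 days after the last dose, so the half-life is at most 98/5 = 19.6 days. From 27.3 mg/L at 14 days after the last dose, a further 84 days leaves at most 27.3 × 2^(−84/19.6) = 1.4 mg/L for a typical 240 mg subject. At 60 mg this would be about 1.4/4 = 0.35 mg/L if exposure were dose-proportional. Protocol 2.2 reports more than proportional PK, which points lower. Late time points that mix BLQ and measurable values are therefore plausible within the assumed LLOQ range.

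**The case against.** The strongest reply is that the fault is small and partly visible. The concentration tables keep every BLQ as zero and already report its count, so arithmetic mean, median and minimum move down, not up. Time points with almost no measurable values are suppressed. The parameter rule reaches only the intensive subset; the other 28 or so subjects per arm (38 − 10) appear in concentration tables with BLQ as zero. Lost troughs can be seen by comparing N with n. No BLQ rate is given, the 2-of-10 case is hypothetical, and SAP 9.2 plans no analysis of ADA by exposure. All of this stands, and it limits the point. It does not supply the missing rule for zeros or return BLQ troughs to the Ctrough summary.

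Three stronger readings are tempting, and the documents do not support them.
- **That the SAP drops BLQ subjects from the geometric mean.** It does not say so. That is one possible software behaviour; taken literally, the rule gives zero or no value.
- **That exposure is overstated throughout the PK output.** Upward bias follows from the text only for the NCA Ctrough summary. It would reach the concentration-table geometric mean only if zeros were discarded.
- **That measurable data after dose 6 are erased.** The consecutive-BLQ rule sits in the list for individual graphs. Tables and NCA have separate rules without it.

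**Conclusion.** Both faults hold as stated. In SAP 9.1.1 the geometric mean and geometric CV have no valid definition at any time point with at least one BLQ and at least three measurable values. In SAP 9.1.2 BLQ troughs after the first dose leave the intensive-subset Ctrough summary, and its arithmetic mean is inflated by n/(n−k) relative to BLQ as zero. That ratio is exact for any k, but how many BLQs will occur cannot be derived from the documents.

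The practical reach is the lower doses, washout samples (for the concentration tables), and subjects who lose exposure, for example through ADA or missed doses. Predicted 240 mg steady-state troughs are practically out of reach. The outputs are exploratory and descriptive, and no primary or secondary efficacy result depends on them. The correction is still worth making before the PK tables are programmed, because the affected summary is the one that would be set against the trough target in Protocol 4.3.2.

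**What to change.** - **SAP 9.1.1, tables.** Keep BLQ as zero for arithmetic mean, median and minimum. Report geometric mean and geometric CV as NC at any time point with a BLQ value, or compute them with BLQ set to LLOQ/2 and say so in a footnote. Choose one option in advance. The BLQ count already planned stays beside them.
- **SAP 9.1.2, Ctrough.** Keep post-first-dose BLQ troughs in the Ctrough summary as zero. Use the same NC or LLOQ/2 rule for its geometric statistics, and add a BLQ count.
- **Figure 7 and SAP 9.1.3.** State that the same Ctrough rule governs the boxplot and the plot against pain scores.
- **Minor, individual graphs only.** Limit the consecutive-BLQ rule to samples within one dosing interval. Protocol Table 1-2 has only pre-dose samples from Day 15 up to the last dose on Day 71, so two BLQ troughs in a row would otherwise blank real values after the last dose on those graphs.

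The cost is a few SAP sentences and one column in a table shell, with no new data. The drawback is that LLOQ/2 is arbitrary and makes the geometric mean depend on the assay limit (13.6 to 18.3 mg/L for one BLQ in ten over the assumed range). The NC option avoids this but leaves no geometric mean at those time points.

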9.1.2 Pharmacokinetic Parameters

PK parameters will be calculated for the intensive PKS by non-compartmental analysis methods from the concentration-time data following these guidelines:

- Actual sampling times relative to dosing rather than nominal times will be used in the calculation of all derived PK parameters.
- There will be no imputation of missing data.
- Handling of BLQ samples for derivation of PK parameters
 - Day 1, all BLQ values pre-dose and in the absorption phase prior to the first quantifiable concentration will be substituted by zeros.
 - For subsequent dosing days, BLQ values pre-dose, in the absorption phase, and between evaluable concentrations will be substituted by missing values before the calculation of the PK variables.
 - BLQs at the end of a participant profile (i.e., after the last incidence of a measurable concentration) will be set to missing.

Pharmacokinetic parameters will be estimated according to the following guidelines:

Parameter	Guideline for Derivation
C_{max} , t_{max} , C_{trough} ,	Obtained directly from the observed concentration-time data
AUC_{0-10d} , AUC_{0-inf} , $AUC_{(0-tau)}$	The AUC_{0-10d} , AUC_{0-inf} , AUC over the dosing interval after the last administered dose will be calculated by a combination of linear and logarithmic trapezoidal methods. Unless specifically requested and justified, the linear up/log down trapezoidal method will be employed.
%AUCextrap	Percentage of AUC_{inf} (obs, pred) due to extrapolation from t_{last} to infinity: $\%AUCextrap = \frac{AUC_{inf} - AUC_{last}}{AUC_{inf}} * 100$
λ_z , $t_{1/2}$	
1. The apparent terminal phase rate-constant (λ_z) will be estimated by linear regression of concentration versus time data presented in a log-linear scale.
 
2. Data are primarily monotonically decreasing in magnitude and are representative of the actual decline in the log concentration-time curve.
 
3. Only those data points that are judged to describe the terminal log-linear decline will be used in the regression.
 
4. A minimum number of three data points in the terminal phase will be used in calculating λ_z with the line of regression starting at any post-C_{max} data point (C_{max} should not be part of the regression slope). Unless otherwise determined by PK Scientist's best knowledge and judgment, if the adjusted correlation coefficient (R^2 adjusted) is <0.8, it will be excluded from the summary tables and statistical analysis of PK parameters, and λ_z and all the λ_z dependent parameters (i.e., $t_{1/2}$) will also be flagged and excluded from summary tables and statistical analysis. The reason for exclusion will be listed/footnoted in parameter listings.
 
5. Unless otherwise determined by PK Scientist's best knowledge and judgment, the interval used to determine λ_z should be equal or greater than 1.5-fold the estimated $t_{1/2}$, and if less than 1.5-fold, λ_z will be flagged in listings. All the derived parameters (i.e., $t_{1/2}$) will also be flagged from listings of PK parameters. The reason for flagging will be listed/footnoted in parameter listings.
 
6. The $t_{1/2}$ will be calculated as follows: $t_{1/2} = \ln 2 / \lambda_z = 0.693 / \lambda_z$
 
7. Data points may be dropped from the linear regression if the PK Scientist considers the reported values to be anomalous. Any data points so designated should remain in the listings with a footnote and be identified in the study report with a rationale for exclusion.

MRT	
MRT is Mean residence time from the time of dosing to the time of the last measurable concentration.
 
For non-infusion models:
 $MRT = \frac{AUMC_{last}}{AUC_{last}}$
CL/F	
Total body clearance for extravascular administration, calculated as follows:
 $CL/F = \frac{dose}{AUC_{0-inf}} \text{ (non-steady state) or } CL/F = \frac{dose}{AUC_{0-tau}}$
V_z/F	
V_z/F is Volume of distribution based on the terminal phase.
 
For non-steady state:
 $V_z/F = \frac{dose}{\lambda_z * AUC_{0-inf}}$ 
For steady state:
 $V_z/F = \frac{dose}{\lambda_z * AUC_{0-tau}}$

Parameter	Guideline for Derivation
R_{ac}	Accumulation ratio, calculated from comparison of first dose and last dose: Based on C_{max} : $R_{ac} = \frac{C_{max}(\text{last dose})}{C_{max}(\text{first dose})}$ Based on AUC: $R_{ac} = \frac{AUC_{(0-\tau)}(\text{last dose})}{AUC_{(0-\tau)}(\text{first dose})}$

PK parameters will be listed by subject for the PKS. PK parameters that will be excluded from summary tables and statistical analyses of PK parameters will be flagged and footnoted with the reason for exclusion.

PK parameters will be summarized by dose cohort for the extensive PKS. Summaries for PK parameters will report N (number of subjects who received treatment) and n (number of subjects with non-missing values). Descriptive statistics for calculated PK parameters will include N, n, arithmetic mean, SD, CV%, Geomean, gCV%, median, minimum, and maximum values. For t_{max} , only N, n, median, minimum and maximum values will be presented. No descriptive statistics will be determined when fewer than three individual PK parameters are available.

The rules followed for presentation of PK parameters data with regards to the number of decimal places/significant digits for the listings of participant level PK parameters and summary tables of PK parameters are as follows:

PK Parameter Listings and Tables	Rounding
Derived Individual parameters	4 s.f.
Directly Derived Individual parameters (C_{max} , C_{trough})	n s.f. as supplied by the WinNonlin but not more than 4 s.f.
Minimum and Maximum	4 s.f.
Mean/SD/Median/Geomean	4 s.f.
CV%/gCV%	1 d.p.
N/n	Whole number
Exceptions for PK Tables	
t_{max} individuals and min/max	2 d.p.
t_{max} median only	2 d.p.

s.f. = significant figures, d.p.= decimal place

